8. PHARMACODYNAMICS/TARGET ENGAGEMENT AND MOTOR FUNCTIONS

8.1 Pharmacodynamic/Target Engagement (Exploratory):

All participants will undergo two needle muscle biopsies during the study in order to determine S 48168 (ARM210) PD in the RYR1-RM population. Biopsy 1 will take place pre-dose during study visit 1 (Day -1/Day 1, pre-treatment). Biopsy 2 will take place during study visit 3 (Day 27/28, post-treatment). Baseline (pre-treatment) and

post-treatment biopsies will be assayed for RyR1-Calstabin1 interaction as % RyR1-Calstabin1 binding of normal control muscle. % RyR1-Calstabin1 binding will be listed by subject with summary statistics calculated to compare between pre- and post-treatment biopsy results.

If there is sufficient remaining tissue, % Ca^{2+} leak from RyR1 will be determined and listed by subject and compared between pre- and post-treatment biopsies.

8.2 Motor Functions and Quality of Life (Exploratory):

Timed Functional Tests: Timed functional tests will be performed on Day -1 (pre-treatment) and Day 27 (post-treatment) and include 10-meter walk test, supine to stand, ascend 4 stairs, and descend 4 stairs. The recorded time will be listed by subject and summarized descriptively for each test to compare between pre- and post-treatment biopsy results.

Grip/Pinch Strength: Day -1 versus Day 27 hand grip and pinch strength will be documented quantitatively using dynamometry. This will also be assessed at trial mid-point (Day 14). The results will be listed by subject and summarized descriptively to compare hand grip and pinch strength (kg) between pre- and post-treatment.

Motor Function Measure 32:

Day -1 versus Day 27 motor function will be documented quantitatively using the scoring of the MFM32 for the following: total score, domain 1 (standing and transfers), domain 2 (axial and proximal motor function), and domain 3 (distal motor function). The resulting scores will be listed by subject and summarized descriptively to compare between pre- and post-treatment.

Quality of Life Questionnaire: PROMIS-fatigue subscale questionnaires will be completed by participants during study visits 1 (Day -1), 2 (Day 14), and 3 (Day 27) with a raw score, theta, t-score, and standard error reported. All results will be listed by subject and summarized descriptively, as applicable, to compare between pre- and post-treatments.

8.3 Clinical Laboratory Tests (Serum Chemistry, Hematology, Urinalysis)

Serum chemistry, hematology and urinalysis tests will be performed at Screening and on Days 14, 27 and 35 (Follow-up).

Out-of-range values and corresponding recheck results will be listed.

For all numeric laboratory values, descriptive statistics will be presented for each laboratory test by assessment time point and treatment. Change from baseline will be summarized in a similar manner. Baseline is defined as the screening result closest

and prior to first dose which may include unscheduled or recheck results. Postdose unscheduled event and recheck results will not be included in summaries.

For each laboratory test, a shift table will be developed to compare the frequency of the results at baseline (above normal, normal, or below normal) with the respective postdose results.

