11.6.3 Early Termination of Subjects from the Study

All participants have the right to withdraw from the study at any time.

In addition, subjects may be withdrawn from the study by the PI or designee for the following reasons:

- AEs.
- Subject has a positive urine drug or alcohol result.
- Difficulties in blood collection.
- Pregnancy.
- Disease progression which requires discontinuation of the study intervention.
- If the participant meets an exclusion criterion (either newly developed or not previously recognized) that precludes further study participation.

The PI, in consultation with the Medical Monitor, may withdraw any subject from the study treatment, if, in the investigator's opinion, it is not in the subject's best interest to continue. A subject may be withdrawn by the PI (or designee) or the Sponsor/Medical Monitor if enrollment into the study is inappropriate, the study plan is violated, or for safety reasons.

If withdrawn from the study, participants will be required to return all remaining study drug. A mailing address will be provided to the participant upon withdrawal. If withdrawn, the participant will still need to provide a blood sample locally and have a remote TEAE assessment 7 ± 2 days post-withdrawal from the study. A study investigator will contact participants by telephone to remind them of upcoming, scheduled local phlebotomy appointments. The participant will also need to have a remote TEAE assessment 14 ± 2 days post-withdrawal from the study. Participants local to the study site will have the option of completing AE assessments at the NIH. If a participant is withdrawn for a safety reason(s), more intensive safety monitoring may be undertaken as clinically indicated.

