6. SAFETY

All case report form (CRF) data will be listed by subject and chronologically by assessment time points. This will include rechecks, unscheduled assessments, and early termination.

Applicable continuous variables will be summarized using n, arithmetic mean, SD, minimum, median, and maximum. Frequencies and percentages will be used to summarize categorical variables.

The level of precision will be presented as follows: minimum/maximum in the same precision as in the database, mean/median in one more precision level than minimum/maximum, SD in one more precision level than mean/median, and n will be presented as an integer.

Where individual data points are missing because of dropouts or other reasons, the data will be summarized based on reduced denominators.

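### Laboratory, vital-sign and ECG summaries leave out post-dose unscheduled and recheck results, and no worst-post-dose display is planned to bring them back in

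*SAP*

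**What the plan says.** SAP 8.3 summarises laboratory tests by time point and treatment: Screening, Days 14 and 27, and a Day 35 follow-up. It then states: "Postdose unscheduled event and recheck results will not be included in summaries". SAP 8.4 (vital signs) and 8.5 (ECG) repeat that sentence.

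The baseline is treated differently. In SAP 8.3 it is the screening result closest "and prior to first dose which may include unscheduled or recheck results". SAP 8.4 allows the same for vital signs. SAP 8.5 defines no ECG baseline.

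The shift-table sentence follows the exclusion in SAP 8.3: "For each laboratory test, a shift table will be developed to compare the frequency of the results at baseline", graded as above, within or below normal, "with the respective postdose results". It does not say whether off-schedule results count.

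Other relevant provisions:
- SAP 6 lists all CRF data, including rechecks, unscheduled assessments and early termination. For summaries it says: "Where individual data points are missing because of dropouts or other reasons, the data will be summarized based on reduced denominators".
- SAP 8.3 adds: "Out-of-range values and corresponding recheck results will be listed". Tables 14.3.4.1 to 14.3.4.3 do this in Section 14 of the report.
- SAP 6.3 and Table 14.3.1.4 tabulate treatment-emergent AEs of grade 2 or higher, all serious AEs and all AESIs, with no visit restriction.
- Protocol 12.10.6 allows unscheduled laboratory tests when the investigator judges them necessary.
- Protocol 11.6.3 states: "If withdrawn, the participant will still need to provide a blood sample locally and have a remote TEAE assessment", timed 7 ± 2 days after withdrawal.

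**The concern.** For-cause testing is where an emerging abnormality is most likely to be chased, and these are the results the summaries leave out. The baseline can draw on an unscheduled or recheck value while the post-dose side cannot, so the two sides of a change score are selected by different rules.

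Safety is the primary objective, the analysis is descriptive, and the protocol targets about 8 to 20 completers. One subject is therefore a visible share of any table. If that subject's abnormal value is off-schedule, the laboratory table can show no abnormality while the AE table or a listing shows one, and the reader has to reconcile them by hand. Listings show the value but give no rate or denominator. Changes below the AESI thresholds, and changes in blood pressure or QTcF, reach an AE table only if someone reports them as AEs.

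**Working it through.** The plan states no figure to reproduce. The check is of where a value would appear, followed by arithmetic for scale.

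**1. How much of dosing the scheduled draws cover.** SAP 8.3 has on-treatment draws on Days 14 and 27, which is 2 of 28 dosing days (2/28 = 7%). Assume a ±2-day window around each, cut off at Day 28. That gives Days 12 to 16 (5 days) and 25 to 28 (4 days), so 9/28 = 32%. A for-cause draw on any other day is unscheduled.

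**2. Where an off-schedule abnormal laboratory value appears.**

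| Display | Included? |
|---|---|
| By-visit summary and change (Tables 14.3.5.1, .3, .5) | No (SAP 8.3) |
| Shift tables (14.3.5.2, .4, .6) | Not stated |
| Out-of-range and recheck tables (14.3.4.1 to 14.3.4.3) | Yes |
| Subject listings | Yes (SAP 6) |
| AE and AESI tables (14.3.1.1 to 14.3.1.4) | Yes, if reported as an AE or meeting the AESI definition |

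Vital signs and ECG (Tables 14.3.5.7 and 14.3.5.8) follow the first row. They have no shift table and no out-of-range table, although SAP 8.5 flags QTcF above 450 msec in the listing.

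**3. Illustration.** Assumptions: one subject is normal at baseline, that subject's only abnormal value is off-schedule, nobody else shifts, and the shift table follows the exclusion. Proportion = x/n, with exact (Clopper-Pearson) 95% limits. For x = 0 the upper limit is 1 − 0.025^(1/n).

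| Dosed | By visit, subject attends | By visit, subject misses that visit | Any time post-dose |
|---|---|---|---|
| 3 | 0/3 (0 to 70.8%) | 0/2 (0 to 84.2%) | 1/3 = 33.3% (0.8 to 90.6%) |
| 8 | 0/8 (0 to 36.9%) | 0/7 (0 to 41.0%) | 1/8 = 12.5% (0.3 to 52.7%) |
| 20 | 0/20 (0 to 16.8%) | 0/19 (0 to 17.6%) | 1/20 = 5.0% (0.1 to 24.9%) |

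Three is the size of each dose group treated so far, 8 is the sample size in Protocol 13.2.1, and 20 is the top of the target range. The intervals overlap heavily, so the point concerns what the table displays and not statistical inference.

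**4. The post-withdrawal sample.** Take a withdrawal on Day 10. The Protocol 11.6.3 sample falls on Day 10 + 7 ± 2, that is Days 15 to 19. SAP 3 places its own follow-up draw 7 ± 2 days after cessation of drug, and SAP 8.3 calls the Day 35 draw Follow-up. The interval is the same, so Follow-up is the natural home. But Days 15 and 16 also lie inside the Day 14 ± 2 window of Protocol 11.1, and the SAP has no visit-window rule. The assignment can be inferred but is not written down.

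**The case against.** The strongest reply is that little is lost. The primary endpoint is counted in the AE, serious AE and AESI tables, which this rule does not touch; a transaminase rise meeting the AESI criterion counts whenever it was drawn. Out-of-range laboratory values and rechecks have their own Section 14 tables, and with so few participants a reviewer can read every one. By-visit summaries are also what Protocol 13.3 asks for, since it summarises by time of collection. All of this stands, and it limits the point to a gap in the supporting summaries.

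Several stronger readings are tempting but not supported:

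- *All safety summaries drop these values.* The exclusion is stated only for laboratory, vital-sign and ECG data.
- *The shift tables exclude them.* That is a plausible reading, because a shift table is a kind of summary, but the SAP does not say so.
- *The values that make someone stop drug are missing.* This is true only of values drawn off-schedule. If a scheduled draw is abnormal and a recheck follows, dropping the recheck leaves the abnormal result in.
- *Someone who stops drug leaves the denominator.* Protocol 11.8.5 halts dosing and allows it to resume, and does not cancel visits. Protocol 11.1 applies the Day 14 safety draw to early terminators too, so a loss at Day 14 cannot be assumed.
- *The post-withdrawal sample is discarded.* The protocol requires it, it matches the SAP follow-up interval, and SAP 6 names early termination separately from unscheduled assessments.

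The reply does not show that a by-visit summary answers the question a safety reader asks, namely how many subjects ever had an abnormal value after dosing. No planned laboratory, vital-sign or ECG summary gives that count if off-schedule values are left out.

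**Conclusion.** The point holds as a gap in the laboratory, vital-sign and ECG summaries, with two matters left unstated: whether shift tables use off-schedule results, and which time point receives the post-withdrawal sample. It is a cheap improvement to supporting displays. It does not affect the primary endpoint, and no values are lost from the report.

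The step 3 differences (12.5 percentage points at 8 dosed, 33 in a group of 3, 5 at 20) rest on that step's assumptions. They compare a by-visit count with an any-time count. Both are legitimate quantities, and the any-time count is the one the plan lacks. If shift tables do take in off-schedule results, the gap narrows to the laboratory by-visit and change summaries and to vital signs and ECG. The documents give no basis for estimating how often an abnormal value would first appear off-schedule.

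**What to change.** Keep the by-visit summaries as planned, and make these changes:

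1. In SAP 8.3 to 8.5 and Tables 14.3.5.1 to 14.3.5.8, add a row for each subject's worst post-dose value (highest, and lowest where relevant) from first dose to end of follow-up. Include unscheduled, recheck and early-termination results, and show change from baseline. For ECG, state the baseline first.
2. For laboratory tests, add a worst-post-dose shift row. For AST and ALT, shift by the ULN multiples the protocol already uses for the AESI (3 and 5 times ULN).
3. Use as denominator all dosed subjects with any post-dose result.
4. State whether the by-visit shift tables use off-schedule results.
5. Assign the Protocol 11.6.3 sample to the Follow-up time point.
6. Define end of follow-up. Protocol 11.1 now has an on-site Day 42 visit with safety laboratory tests that SAP 8.3 does not list.

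The cost is SAP wording and an extra row or so per table, from data already collected. SAP 11 and 11.2 say the safety table shells are still to be written. There is one downside: worst-value rows run higher in people who are tested more often. They should therefore sit beside the by-visit rows and not replace them.

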Participants will be contacted by a study investigator by telephone and/or e-mail four times during the study for AE assessments. The investigator will ask a series of open-ended and focused questions relating to safety and tolerability of S 48168 (ARM210). On rare occasions, additional participant contact may be made by telephone or secure email to ensure comprehensive monitoring. Examples include contacting participants to inform them of important new safety-related information, changes in key study personnel, and clarification of medical information.

AEs (whether serious or non-serious) and clinically significant abnormal laboratory test value(s) will be evaluated by the PI or designee and treated and/or followed up until the symptoms or value(s) return to normal, or acceptable levels, as judged by the PI or designee.

Treatment of SAEs will be performed by a licensed independent provider, either at NIH CC or at a nearby hospital emergency room. Where appropriate, medical test(s) and/or examination(s) will be performed to document resolution of event(s). Outcome may be classified as resolved, improved, unchanged, worse, fatal, or unknown (lost to follow-up).

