12.10.7.7 AE's of Special Interest

An AE of Special Interest (serious or nonserious) is one of scientific and medical concern specific to the compound or program, [REDACTED]

AEs of special interest in this trial include:

- Large increases in transaminases, Aspartate aminotransferase or Alanine aminotransferase. If the subject's baseline transaminases were within normal limits, then a change of 3X ULN is the criteria. If the subject's baseline transaminases are above the ULN at baseline, then 5X ULN would be the criteria. Baseline elevations in transaminases have been known to occur in some patients with *RYR1*-RM, likely due to muscle injury as a consequence of the disease and normal activity.
- CNS toxicity (tremors/convulsions seen in safety assessment animals) - consider tremors and any symptoms of seizure as the events to monitor for.
- Gastric toxicity - severe gastric or epigastric pain or severe vomiting.
- Plasma Cmax (S 48168) >35 µg/mL.

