2.2 Endpoints

Primary:

Composite safety and tolerability profile

(Frequencies of the following: TEAEs \geq grade 2 in severity (CTCAE version 5), all SAEs, and all AESIs).

Methods: Safety and tolerability of S 48168 (ARM210) will be determined by monitoring Adverse Events (AEs) over 28 days of treatment via patient interviews, patient diary reviews, physical examinations, echocardiograms, electrocardiograms (ECGs), vital signs, and laboratory safety tests. A reference dataset of AEs/SAEs obtained from a natural history study of RYR1-RM will also be available to assist in interpretation of safety events. The Columbia-Suicide Severity Rating Scale (C-SSRS) will also be administered pre- and post-intervention. The frequency and severity of clinically significant AEs will be compared between treatment and historical controls including a previously conducted natural history study at the NIH.

Exploratory:

1. To determine PK of a 28-day administration of S 48168 (ARM210) in RYR1-RM affected individuals.

Endpoints:

Day 1: AUC_{0 t}, AUC_{0 inf}, C_{max}, T_{max}, and t_{1/2}

Day 28: AUC_{tau}, C_{max}, T_{max}, C_{min}, RAAUC, and RAC_{max}

Secondary PK parameters will include: AUC₀₋₂₄, AUC%extrap, T_{min}, K_{el}, T_{lag}, and Day 13 C_{trough} (associated with Day 14 pre-dose). Additional parameters may be calculated as appropriate.

Methods: Bloods for PK assessments will be drawn at baseline (Day 0, 24h PK), at the study mid-point (day 14 \pm 2 days, trough PK), and at the final study visit (Day 28, 24h PK). Whole blood will be processed, and the plasma fraction stored for batch PK analyses.

2. To explore if S 48168 (ARM210) treatment increases RyR1-calstabin1 binding in skeletal muscle of RYR1-RM affected individuals.

Endpoint: Change from baseline in relative RyR1-calstabin1 binding (AU) and (pending sufficient tissue yield) change from baseline in relative Fluo-4 signal (AU).

Methods: Skeletal muscle tissue will be obtained from participants pre- and post-intervention by needle biopsy. This tissue will be assessed for RyR1-calstabin1

binding by co-immunoprecipitation followed by protein detection. The percentage of Calstabin1 binding to RyR1 pre-dose will be compared to the percentage obtained post-dose in each patient. Pending sufficient tissue yield, muscle membrane preparations may be assessed for changes in calcium permeability (Fluo-4 signal) using a thapsigargin assay.

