6.3 Adverse Events

All adverse events (AEs) reported during this clinical trial will be coded using the Medical Dictionary for Regulatory Activities (MedDRA[®]), Version 21.0.

All adverse events will be reviewed by the Medical Monitor and graded in accordance with CTCAE version 5

(https://ctep.cancer.gov/protocoldevelopment/electronic_applications/ctc.htm)

All AEs captured in the database will be listed in by-subject data listings including verbatim term, coded term, treatment, severity, relationship to study medication, and action; however, only treatment-emergent AEs (TEAEs) will be summarized.

A TEAE is defined as an AE that is starting or worsening at the time of or after study drug administration. Each TEAE will be attributed to a treatment based on the onset date and time of the AE.

An AE will also be considered treatment emergent if: onset date of an AE is missing; if onset time of an AE is missing and the onset date is the same as the treatment dosing date; and if both AE onset date and time are missing.

TEAEs will be tabulated by System Organ Class (SOC) and Preferred Term (PT). Summary tables will include number of subjects reporting the AE and as percent of number of subjects dosed by treatment and study overall. The number of AEs will be tabulated in a similar manner. Tables which tabulate the number of TEAEs by severity and relationship to study treatment will also be included.

Serious adverse events (SAEs), if present, will also be listed. Applicable narratives will be included in the CSR.

Frequencies of TEAEs \geq grade 2 in severity (CTCAE version 5), all SAEs, and all AE of Special Interest (AESI) will be tabulated by SOC/TE.

The frequency and severity of clinically significant AEs will be compared descriptively between treatment and historical controls including a previously conducted natural history study at the NIH.

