14.3 Safety Data Summary Tables

14.3.1 Displays of Adverse Events

Table 14.3.1.1 Treatment-emergent Adverse Event Frequency by Treatment – Number of Subjects Reporting the Event (% of Subject Dosed) (Safety Population)

Table 14.3.1.2 Treatment-emergent Adverse Event Frequency by Treatment – Number of Adverse Events (% of Total Adverse Events) (Safety Population)

Table 14.3.1.3 Treatment-emergent Adverse Event Frequency by Treatment, Severity, and Relationship to Drug – Number of Adverse Events (Safety Population)

Table 14.3.1.4 Frequency of Treatment-emergent Adverse Event with Grade 2 or Greater Severity, are Serious, or Are of Special Interest by Treatment (Safety Population)

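### The SAP counts the transaminase AESI, part of the primary endpoint, only through reported AEs; no planned laboratory output counts participants who meet the protocol's 3X/5X ULN criterion

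*SAP*

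**What the plan says.** SAP 2.2 defines the primary endpoint as the frequencies of TEAEs of at least "grade 2 in severity (CTCAE version 5), all SAEs, and all AESIs". SAP 6.3, the adverse events section, says that "all AE of Special Interest (AESI) will be tabulated by SOC/TE". The matching output, Table 14.3.1.4, is an AE frequency table for events "with Grade 2 or Greater Severity, are Serious, or Are of Special Interest by Treatment".

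Protocol 12.10.7.7 defines the transaminase AESI numerically. The limit is 3X ULN, worded as a change, when baseline is within normal limits, and 5X ULN when baseline is already above ULN. Protocol 11.8.5 repeats the definition. Protocol 12.10.7.7 also says "Baseline elevations in transaminases have been known to occur in some patients with" this disease. The SAP does not restate the criterion.

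For laboratory data, SAP 8.3 plans a shift table to "compare the frequency of the results at baseline (above normal, normal, or below normal) with the respective postdose results", and adds: "Postdose unscheduled event and recheck results will not be included in summaries". The same section plans descriptive statistics and change from baseline for each numeric test by time point and treatment, and a listing of out-of-range values with their rechecks. SAP 6 gives the statistics for continuous variables, including minimum and maximum, and plans by-subject listings of all CRF data, with unscheduled assessments and rechecks.

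**The concern.** This AESI can be decided from data already in the database: a baseline value, a post-dose value and a ULN. The SAP does not use those data to decide it. A participant enters this part of the primary endpoint only if someone records the value as an AE and the AE is identified as an AESI. The SAP describes no step that checks laboratory values against the AE records for this purpose.

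The shift table is the laboratory output a reader would turn to for this, and it cannot show either threshold. It is least informative for participants with a raised baseline, for whom the 5X limit was written. A peak found only at an unscheduled or recheck draw is absent from every laboratory summary table.

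The trial is small and safety is its primary question, so a single uncounted case would change the reported frequency visibly.

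**Working it through.** The plan gives no figure to reproduce. The check classifies hypothetical values under the plan's own rules.

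**Inputs**
- AESI limits: 3X ULN (normal baseline) and 5X ULN (raised baseline), protocol 12.10.7.7.
- Raised baselines are eligible: exclusion criterion 6 (protocol 11.6.2) starts at three times ULN for ALT and five times for AST.
- Shift categories: below, normal, above (SAP 8.3).
- Scheduled post-dose chemistry: Days 14, 27 and 35 (SAP 8.3).

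**Step 1: shift category against AESI criterion.** Values are multiples of ULN. The limit is read first as a level reached (post-dose value at or above 3 or 5), then as a rise (post-dose minus baseline at or above 3 or 5).

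| Baseline | Post-dose | Shift table | AESI as level | AESI as rise |
|---|---|---|---|---|
| 0.8 | 1.2 | normal to above | no | no |
| 0.8 | 3.5 | normal to above | yes | no (2.7) |
| 0.8 | 4.0 | normal to above | yes | yes (3.2) |
| 1.5 | 1.6 | above to above | no | no |
| 1.5 | 6 | above to above | yes | no (4.5) |
| 2.5 | 7.6 | above to above | yes | yes (5.1) |
| 2.9 | 12 | above to above | yes | yes (9.1) |
| 4.8 (AST) | 5.1 | above to above | yes | no (0.3) |

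All five raised-baseline rows fall in one cell and read as no shift. From a normal baseline, a trivial rise and one that meets the criterion also share a cell. The two readings of the limit disagree in three of the eight rows.

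**Step 2: what the numeric tables add.** Let one participant go from 2.5 to 6 at a scheduled visit while the others do not change. The maximum value is 6 and the maximum change is 6 − 2.5 = 3.5. The mean change is 3.5/n:
- n = 3: 1.17
- n = 6: 0.58
- n = 8: 0.44
- n = 20: 0.18

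The maxima therefore reveal a scheduled rise, but they do not count cases. Under the level reading, a maximum between 3 and 5 times ULN qualifies if that participant's baseline was normal and does not if it was raised. The table does not link the two. A maximum also says nothing about how many participants qualified.

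**Step 3: unscheduled or recheck peak.** If the value of 6 occurs only at such a draw, it is in neither the shift table nor the numeric table. It appears in the listings. It reaches Table 14.3.1.4 only through an AE record.

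**Step 4: scale of one uncounted case.** 1/8 = 12.5 percentage points for the sample size in protocol 13.2.1. 1/3 = 33 points for the three participants dosed so far at each level (protocol 11.1). These figures show what one case would do, not how likely it is.

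**The case against.** Three stronger readings are tempting, and the documents support none of them.

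**That the laboratory outputs conceal the rise.** They do not. Table 14.3.5.1 gives numeric and change-from-baseline summaries for serum chemistry. Table 14.3.4.1 lists out-of-range values with rechecks, and Appendix 16.2.8.1.1 is a chemistry listing. Unscheduled and recheck values are excluded from summaries, not from the report. In a descriptive study with about 8 to 20 completers, listings are a main safety output. A recheck also follows an initial result, and if that result was scheduled it stays in the summaries.

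**That an investigator may leave out a qualifying value as not clinically significant.** Protocol 12.10.7.3 says "clinically significant abnormal laboratory test value(s) will be evaluated by the PI or designee", but that sentence concerns evaluation and follow-up. It does not make clinical significance a condition for an AESI. Protocol 12.10.7.7 sets a numeric criterion and treats AESIs as AEs. Protocol 12.10.7.4 requires all AEs to be recorded, reviewed with the medical monitor and reported to the DSMB whatever the investigator's classification.

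**That the AESI count will be too low.** This is possible but not shown. Unscheduled tests are drawn because someone judged them necessary (protocol 12.10.6), so that participant is already being watched. Part of the AESI text is redacted, the medical monitoring plan is not among the documents reviewed, and the safety table shells are deferred (SAP 11). Protocol 14.5 describes general edit checks for inconsistencies.

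What remains is narrower. The recording and review safeguards act once an AE has been entered. No document reviewed names a check that every qualifying laboratory value became an AE. A listing is not a frequency, and the endpoint is a frequency.

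**Conclusion.** The point holds in limited form. SAP 6.3 and Table 14.3.1.4 count the transaminase AESI only through reported and coded AEs. The SAP states no derivation from laboratory data and no reconciliation. The three-category shift table cannot show either AESI threshold, and the other planned laboratory outputs show some cases without counting them. The frequency is correct if every qualifying value is recorded as an AE and identified as an AESI, and too low otherwise. The documents do not let the chance of that be estimated.

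The conclusion assumes that raised baselines will occur, which the protocol expects and its eligibility criteria allow. It also assumes that the deferred safety shells and the medical monitoring plan do not already supply the missing rule. This is an inexpensive improvement to make before the tables are programmed, not evidence that the planned result is wrong.

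**What to change.** 1. **Definition first.** The sponsor should state whether the 3X limit means a level reached or a rise from baseline, and whether the 5X limit is read the same way. The wording should be made consistent in protocol 11.8.5 and 12.10.7.7. Which reading is right is a clinical decision for the sponsor. Until it is made, the flag cannot be programmed.
2. **SAP 6.3.** Flag by program every participant with a post-dose AST or ALT value, scheduled, unscheduled or recheck, that meets the criterion for that participant's baseline. Reconcile the flags with the AE records and show the count with Table 14.3.1.4. SAP 8.5 already flags a numeric threshold for QTcF, so the approach is not new to this plan.
3. **SAP 8.3.** For AST and ALT, add or substitute a shift from baseline to worst post-dose value, in multiples of ULN or CTCAE grade, using all post-dose values. Keep the by-visit summaries on scheduled values.

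The cost is SAP wording, a clarification of the protocol definition and one extra derivation. No new data are needed. The reported AESI count may rise slightly.
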